## 8 Design

The **STOP-IT** trial is designed as a pragmatic, multi-centre, randomised, controlled, open-label, superiority study with two parallel groups and primary endpoints of opioid positivity and healthcare utilization at 12 months after enrollment. Randomization will be performed with a 1:1 allocation ratio using a stratified, permuted-block group schema according to the following strata (no fixed ratio):

- 1) RAAM clinic site (Barrie, Orillia, Midland, Wasaga Beach)
- 2) Severity of OUD according to DSM-V criteria (moderate vs severe)

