## 10.1 Inclusion criteria

Patients eligible for the trial must comply with all of the following at randomization:

1. Ages 18 to 65 years old
2. OAT indicated for moderate- to severe-[OUD](#)
3. Attend a RAAM clinic in the North Simcoe Muskoka Local Health Integrated Network for opiate substitution treatment
4. Successfully completed induction and stabilization OAT with [Suboxone](#)® tablet or film defined as receiving 8mg/2mg to 24mg/6mg of [Suboxone](#)® for  $\geq 7$  days with no evidence of allergic reaction to [Suboxone](#)®, [Clinical Opiate Withdrawal Scale](#) (COWS) score  $\leq 12$  (scale:0-48) for  $\geq 24$  hours, and [Opiate Craving Visual Analog Scale](#) (VAS) score  $\leq 20$  (scale:0-100) for  $\geq 24$  hours
5. Must have an active Ontario Health Insurance Plan number
6. Must have a telephone that can receive calls, text messages or emails
7. Must have drug insurance coverage for either medication for duration of study or demonstrate ability to pay for the drug out-of-pocket

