## 12 Outcomes

### 12.1 Primary outcome measures

#### 12.11 Opioid positivity

Difference in proportions of relapse-free weeks (RFWs) at 12-months from the date of randomization, where ***relapse-free weeks are defined by the cumulative number of weeks alive during the study period in which there was a negative urine drug screen and negative self-report for non-prescribed opioids.*** The potential number of RFWs for each patient is the cumulative number of weeks that the patient is alive during the 12-month study period, with a maximum of 48 weeks. A week is defined as a consecutive 7-day period starting on the day of the week that randomization occurred. A patient is considered to have 'completed' a week as long as they are alive for  $\geq 1$  day of that week. For example, if a patient is randomized on a Tuesday, and subsequently dies on a Thursday of the 32nd week, the patient will have been considered to have been alive for 32 weeks. The denominator used in estimating the proportion of RFWs will be the total number of weeks that the patient was alive during the study period. Vital statistics for all participants (date and year of death) will be available through linkage with the Office of the Registrar General of Ontario database. The cumulative number of RFWs alive will be used as the numerator in estimating the proportion of RFWs. Scheduled urine drug testing and self-reports will occur every 2 weeks during the study period starting in week 2 from randomization. Imputation of missing data will occur for those weeks in which a urine drug screen/self-report was not scheduled according to the results of the subsequent week's urine drug screen/self-report. For example, if a urine drug screen/self-report was not scheduled for week 11, but a scheduled urine drug screen/self-report was done on week 12 and week 12 met the criteria for a RFW, then week 11 would be imputed as a RFW (Figure 1). Similarly, for weeks with scheduled urine drug screen/self-reports that are missed, that week and the preceding week in which there was no scheduled urine drug screen/self-report will not be counted as RFWs (for example, see Figure 1, week 17 and 18). In the hypothetical patient represented in Figure 1, 20 urine drug screens/self-reports were completed, with 5 positive and 15 negative urine drug screens/self-reports, resulting in 30 cumulative RFWs over the 48-week study period, or a proportion of RFWs of 0.625.

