# 13 Participant timeline

			Study Period (Weeks)																											
			-1	0	T1	T2	T3	T4	T5	T6	T7	T8	T9	T10	T11	T12	T13	T14	T15	T16	T17	T18	T19	T20	T21	T22	T23	T24		
Activity	C R F	M R P	w-1	w0	w2	w4	w6	w8	w10	w12	w14	w16	w18	w20	w22	w24	w26	w28	w30	w32	w34	w36	w38	w40	w42	w44	w46	w48		
Enrollment																														
Expressed Consent	N	HCP	X																											
Eligibility Screen	Y	HCP SC	X																											
Informed Consent	N	HCP SC	X																											
Randomization	Y	SC		X																										
Demographics	Y	HCP		X																										
Pregnancy test	Y	HCP	X																											
EKG	Y	HCP	X																											
Bloodwork	Y	HCP	X																											
Interventions																														
Suboxone®	Y	HCP		X																										
Sublocade®	Y	HCP		X		X		X		X		X		X		X		X		X		X		X		X		X		
Counselling	Y	HCP		X	X	X	X	X		X		X		X		X		X		X		X		X		X		X		
RAAM clinic visit	Y	HCP		X	X	X	X	X		X		X		X		X		X		X		X		X		X		X		
Pre-clinic visit phone call	Y	HCP SC		X	X	X	X	X		X		X		X		X		X		X		X		X		X		X		
Assessments																														
General exam	Y	HCP		X	X	X	X	X	X	X	X	X	X	X	X	X	X	X	X	X	X	X	X	X	X	X	X	X	X	X
Urine drug test	Y	HCP	X	X	X	X	X	X	X	X	X	X	X	X	X	X	X	X	X	X	X	X	X	X	X	X	X	X	X	X
Timeline Followback	Y	HCP	X	X	X	X	X	X	X	X	X	X	X	X	X	X	X	X	X	X	X	X	X	X	X	X	X	X	X	X
MSQ	Y	HCP SC					X			X			X			X			X			X			X			X		
WHOQOL-BREF	Y	HCP SC		X						X						X						X								X
Pregnancy test	Y	HCP				X		X		X		X		X		X		X		X		X		X		X		X		
SAE	Y	HCP		X																										
EKG	Y	HCP																												
Bloodwork	Y	HCP																												

CRF=case report form; MRP=most responsible person; N=No; Y=Yes; HCP=healthcare provider; SC=study coordinator; EKG=electrocardiogram; MSQ=medication satisfaction questionnaire; WHOQOL-BREF=Quality of life questionnaire; SAE=severe adverse event

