#### 14.4 Final sample size

In a hierarchical 3-level mixed effects model with 45 and 45 level 2 units (RAAM clinic patients) randomized to Suboxone® and Sublocade® in a 1:1 ratio, 4 level 3 units (RAAM clinics) in total and an average of 5 level 1 units (RFWs) per level 2 unit, 90.0% power is achieved to detect a difference in RFWs proportions of at least 0.15, where the Suboxone® and Sublocade® RFWs proportions are 0.3 and 0.45, respectively, assuming that the correlation between level 1 units in a level 2 unit is 0.8 and the correlation between level 2 units in a level 3 unit is 0.025, and the 2-sided test is performed at the 5% significance level. Using even a much smaller sample size (N=20 patients per group with 50% loss-to-follow-up over 12-month study period), a 2-sided comparison of two incidence rates (number of healthcare days per 1000 patient days exposure) with a sample size of 3650 patient days exposure per group would achieve 99% power at the 0.05 significance level to detect a difference in incidence rates of at least 1 if the Suboxone® group incidence rate was 2.

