## 20.11 Primary

### 20.11a Opioid positivity

We will use a 3-level hierarchical design to model the relapse-free weeks data where the observation for each week (Level 1) will be coded as binary; relapse-free week if urine drug screen and self-report is negative for non-prescribed opioid use, and otherwise relapse week if either is positive for non-prescribed opioid use. As described in Section 12.11, imputation of missing data will occur for those weeks in which a urine drug screen/self-report was not scheduled according to the results of the subsequent week's urine drug screen/self-report. Level 1 observations are clustered within individual participants (Level 2), which are nested within RAAM clinic sites (Level 3). We will analyse the outcome data using multi-level, mixed-effects logistic regression analysis with random effects estimated for the variance in the intercepts of both participant and clinic levels. The model will also include a random slope on the indicator for OUD severity (moderate versus severe) in the Level 2 random effects equation using an unstructured covariance structure between intercept and slope. We will also include clinic visit (week) and an interaction term between clinic visit and treatment. A sensitivity analysis will be conducted to compare this baseline model with an extended model that includes any baseline demographic or clinical variables that appear to be unbalanced at Level 1. The models will be compared using the likelihood-ratio comparison test for superiority. Post-regression analyses using *margins* command will be used to estimate difference in proportions of RFWs between treatment groups.

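### The primary opioid model leaves out the opioid result already collected at week 0; prespecifying it as a covariate would gain precision at almost no cost

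*Combined protocol and SAP*

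**What the plan says.** Section 10.1, item 4, requires that patients have "Successfully completed induction and stabilization OAT with" Suboxone. It defines this by a dose range held for at least 7 days, no allergic reaction, and upper limits on the withdrawal and craving scores. Neither Section 10.1 nor Section 10.2 asks for a negative urine test or self-report.

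In the Section 13 timeline, the row "Urine drug test" and the Timeline Followback row are both marked at weeks -1 and 0. Under Section 12.11, "relapse-free weeks are defined by the cumulative number of weeks alive during the study period" with a negative urine screen and self-report, and scheduled assessment begins in week 2. The entry results are therefore not outcome data, although they use the same two instruments.

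Sections 8 and 16.1 stratify by clinic and by DSM-V severity only. The primary model in Section 20.11a has random intercepts for participant and clinic, a random slope on severity, week, and week by treatment. Other baseline variables appear only in a sensitivity analysis, an "extended model that includes any baseline demographic or clinical variables that appear to be unbalanced at Level 1". Section 17 leaves the analysts unmasked.

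**The concern.** The week 0 result is the pre-randomization value of the primary outcome, so it is the natural first candidate for a prognostic covariate. Treatment is assigned to patients, so variation between patients drives the standard error of the treatment effect. The participant random intercept represents that variation but does not explain it; a baseline predictor can.

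Leaving the result out has two consequences. The comparison is less precise than the collected data allow. In addition, if one arm happens to start with more opioid-positive patients, the primary estimate carries that difference. The sensitivity model would address this only after someone had judged the arms unbalanced, with allocation known and without a stated rule.

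**Working it through.** **Inputs from Section 14.4.** There are 45 patients per arm, with "RFWs proportions are 0.3 and 0.45, respectively" (Suboxone, then Sublocade). The average number of measures per patient is m = 5, the within-patient correlation is 0.8 and the within-clinic correlation is 0.025; "the 2-sided test is performed at the 5% significance level".

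**Not in the documents, so assumed.** The share opioid-positive at entry is taken as 30% to 50%. The gap in relapse-free-week (RFW) proportion between entry-negative and entry-positive patients is taken as 0.2 to 0.4. The correlation r of the entry result with a single follow-up result is taken as 0.2 to 0.8.

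**1. Starting power.** Section 14.2's simple figure of 160 per group reproduces: (0.21 + 0.2475) × (1.960 + 0.842)² / 0.15² = 159.6, rounded up to 160. For the final design, Section 14.4 states that "90.0% power is achieved to detect a difference in RFWs proportions of at least 0.15". Taking 45 as the total per arm:

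- mean proportion 0.375, so 2 × 0.375 × 0.625 = 0.46875
- clustering factor (1 + 4 × 0.8 − 5 × 0.025)/5 = 0.815
- SE = √(0.46875 × 0.815/45) = 0.092
- power = Φ(0.15/0.092 − 1.96) = 37%

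The stated 90% does not reproduce on this reading. That is a separate sample-size matter; 37% serves here only as the starting point.

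**2. Chance imbalance at entry.** The SD of the arm difference in entry positivity is √(2p(1−p)/45), which is 0.097 at p = 0.3 and 0.105 at p = 0.5. By the normal approximation, a difference of 10 points or more in either direction occurs in about 30% and 34% of trials. On the outcome scale, this SD is multiplied by the RFW gap. The smallest value is 0.097 × 0.2 = 0.019 and the largest is 0.105 × 0.4 = 0.042, so the 95% range runs from about ±0.04 to ±0.08.

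**3. Gain from adjustment (linear approximation).** The share of the variance of the patient mean that is removed is R² = r² / [(1 + 4 × 0.8)/5] = r²/0.84. The SE is multiplied by √(1 − R²).

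| r | R² | SE | Power | Equivalent sample-size gain |
|---|---|---|---|---|
| none | 0 | 0.092 | 37% | 1.00 |
| 0.2 | 0.05 | 0.090 | 38.5% | 1.05 |
| 0.4 | 0.19 | 0.083 | 44% | 1.24 |
| 0.6 | 0.43 | 0.070 | 58% | 1.75 |
| 0.8 | 0.76 | 0.045 | 92% | 4.2 |

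**4. How the assumptions relate.** The correlation implied by a gap g is roughly g × √(p(1−p)) / √(0.375 × 0.625). With p = 0.3 and g = 0.2 this is 0.2 × 0.458/0.484 = 0.19; with p = 0.5 and g = 0.4 it is 0.4 × 0.5/0.484 = 0.41. The assumed gaps therefore correspond to the second and third rows. At p = 0.5, a correlation of 0.8 would need a gap of 0.8 × 0.484/0.5 = 0.77. With a mean of 0.375 that puts the entry-positive proportion at about 0.375 − 0.39, just below zero. The last row is a ceiling.

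**5. Simulation check.** The simulation used beta-binomial data with 24 visits, 45 per arm, a true difference of 0.15, entry positivity 0.3 to 0.5, gap 0.2 to 0.4 and within-patient correlation 0.5 to 0.8. Over all runs both estimators averaged about 0.15. Adjustment lowered the SD by about 1% to 15% and raised power by about 1 to 13 points. In the 14% to 17% of runs where Sublocade had an excess of at least 10 points entry-positive, the unadjusted mean was 0.08 to 0.13 and the adjusted mean 0.15 to 0.16.

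**The case against.** The strongest reply is that nothing here is an error. Randomization balances entry status on average, the standard error already covers chance imbalance, and covariate choice is a matter of design. That stands: a reader might infer that the planned estimate is biased, but it is not biased over repeated randomizations. The shift in step 2 is conditional on the imbalance that happens to occur.

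A second reply is that the extended model already deals with visible imbalance. This stands only in part:

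- The model is a sensitivity analysis with no threshold for imbalance, and it is chosen by unmasked analysts.
- A likelihood-ratio test compares fit; it does not settle which treatment estimate is primary.
- Section 20.11a defines Level 1 as the weekly observations, whereas baseline variables belong to patients.
- Section 18.11a lists urine toxicology under laboratory data, so it is unclear whether the wording covers it.

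A third reply is that the gain may be negligible. That also stands at the low end. A reader might carry the plan's 0.8 over to the entry result, but Section 14.4 gives that value for follow-up observations only. Nor should a 10-point imbalance in entry status be set directly against the 15-point target, because the two are on different scales.

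Finally, a reader might infer that the run-in criterion, the strata or the word relapse is at fault. The documents do not support this. The dose range and 7-day period match the drug-benefit condition quoted in Section 5.14, the endpoint is defined identically in both arms, and its label changes no estimate. Another binary stratum would turn 8 strata into 16 for 90 patients in blocks of 6. Week 0 is also pre-randomization, not untreated: every patient has by then had at least 7 days of Suboxone.

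**Conclusion.** The point holds as a free improvement, not as a flaw that invalidates the analysis. The plan collects the best available baseline predictor of its primary opioid outcome and gives it no prespecified role in the primary model.

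Under the assumed prevalence and gap, the chance component left in the estimate has an SD of about 0.02 to 0.04, and adjustment would raise power from about 37% to between 38.5% and 44%. Stronger correlations would give more: 58% at 0.6, and 92% at 0.8 as a ceiling. These figures rest on a linear approximation, 45 patients per arm in total, 5 measures per patient and the plan's within-patient correlation of 0.8. The documents fix neither the entry prevalence nor the entry-to-follow-up correlation, so the direction of the benefit is secure but its size is not. Adjustment should not be read as a remedy for the separate sample-size question.

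**What to change.** In Section 20.11a, prespecify the week 0 opioid result as a fixed covariate in the primary model, whatever the observed balance. Code it positive if the urine test, the self-report or both are positive, and use week -1 if week 0 is missing. Week -1 should be only the fallback, because its 7-day recall can reach back before stabilization.

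State that the value used is the one recorded before allocation is released. Section 16.2 already places baseline screening first, but the timeline shows randomization and the week 0 tests in the same column.

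Keep the margins-based difference in RFW proportions as the reported estimate, since adding a covariate to a logistic model changes the meaning of its odds ratio. The existing extended model can remain as a sensitivity analysis for other variables.

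The cost is one model term and a few sentences of text. No data, visits, patients, eligibility criteria or strata are added or changed.

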### 20.11b Healthcare utilization

We will model the days of healthcare utilization as count data, with the period of follow-up while alive during the study period as the exposure period. We will analyse the data using a Poisson regression model. We will include an indicator for OUD severity. We will include any baseline demographic or clinical variables that are unbalanced at Level 1.

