#### 5.1.2 Epidemiology

Opioid use disorder and opioid-related deaths are increasing in Ontario and Canada. Compared to 2016, the age-adjusted opioid-related mortality rates in 2020 have increased by 161% in Ontario to 16.5 per 100 000 population and 114% in Canada to 16.7 per 100 000 population. Over 90% of these deaths were non-intentional, with 87% of all deaths involving fentanyl or fentanyl analogues. The majority of deaths occurred in males (75%) between the ages of 20 to 59 (88%). In the North Simcoe Muskoka Local Health Integration Network, the study region, there were 128 opioid-related deaths in 2020, an increase of 191% from 2016.

Like deaths, opioid-related healthcare utilization as measured by hospitalization and emergency department visits have also been increasing over the same time period. Compared to 2016, the age-adjusted opioid-related hospitalization rates in 2020 have increased by 19.8% in Ontario to 16.3 per 100 000 population and 5.9% in Canada to 17.8 per 100 000 population. Emergency room visits have increased by 166% during the same time period in Ontario to 84.5 per 100 000 population. In the North Simcoe Muskoka Local Health Integration Network, there were 622 emergency room visits and 128 hospitalizations that were opioid-related in 2020. The majority of hospitalizations and emergency room visits occurred in males (60%) between the ages of 20 to 59 (73%). The median length of hospitalization from 2016 to 2020 has remained unchanged at 3 days (Range 1 to 207 days), with an average cost per hospitalization of \$9 626 (CDN) (Range \$26 to \$296 831) (Source: The Ontario Case Costing Initiative; N=889 cases; Reporting period 2017 to 2018; ICD-10-CA codes F11.0 to F11.9 & T40.2; Accessed November 8, 2021).

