#### 12.12 Healthcare utilization

Difference in incidence rates of healthcare days at 12-months from the date of randomization, where **healthcare days represent the number of days alive and registered for an emergency room visit or admitted to an acute care or mental health facility for opioid-related harms or poisonings**. For each group, the incidence rate is calculated by dividing the total number of healthcare days by the total person days exposure over the study period. The potential number of healthcare days for each patient is the number of days alive during the 12-month study period, with the maximum being 365 days. Any day in which a patient is documented to have had an emergency room visit or is admitted to an acute care or mental health facility for any opioid-related harm or poisoning will be counted as a healthcare day. To estimate the number of opioid-related harms and poisonings resulting in healthcare utilization, the Discharge Abstract Database, Ontario Mental Health Reporting System database, National Ambulatory Care Reporting database, Registered Persons Database, and Office of the Registrar General of Ontario database will be linked to each patient's Ontario Health Insurance Plan number and the following opioid-related harms and poisonings International Statistical Classification of Diseases and Related Health Problems, Tenth Revision, Canada (ICD-10-CA) codes will be used to estimate the number of healthcare days utilized during the study period: Y45, F11.0-F11.9, T40.0-T40.4, T40.6. All opioid-related harms and poisonings resulting in the utilization of a healthcare day regardless of intent (ICD-10-CA X42 (accidental), ICD-10-CA X62 (intentional), and ICD-10-CA Y12 (undetermined)) will be included in the final analysis. Only those healthcare days in which opioid use was considered to be influential to the ER visit or hospitalization will be included and are identified by the following ICD-10-CA codes: M (most responsible diagnosis), 1 (pre-admit comorbidity), 2 (post-admit comorbidity), W or X or Y (Service transfer diagnosis). In addition, Diagnostic and Statistical Manual of Mental Disorders, 5th Edition codes 304.00 and 305.50 will be used to capture healthcare days for opioid-related harms and poisonings.

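### Poisson regression on healthcare days makes no allowance for multi-day stays, so the type I error on this primary endpoint exceeds 5% (about 14% with 3-day stays at the regional visit-to-admission mix)

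*Combined protocol and SAP*

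**What the plan says.** Section 12.12 measures the second primary outcome by the day. Its counting rule begins: "Any day in which a patient is documented to have had an emergency room visit or is admitted to an acute care". Stays in mental health facilities qualify too, the reason must be opioid-related, and each such day scores one. Section 20.11b then states: "We will model the days of healthcare utilization as count data", with time alive as the exposure, and "We will analyse the data using a Poisson regression model". The only additions are an indicator for OUD severity and any unbalanced baseline variables. No dispersion parameter, robust variance, negative binomial model or patient-level term is named for this endpoint. By contrast, Sections 20.11a and 20.12 give relapse-free weeks and the questionnaire scores random effects for patient and clinic, and Section 14.2 criticises earlier trials for ignoring clustering.

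On the size of the clumps, Section 5.1.2 says that in the study region "there were 622 emergency room visits and 128 hospitalizations that were opioid-related in 2020", and gives a median hospital stay of 3 days with a range of 1 to 207. Section 14.4 says that 3 650 patient-days per group "would achieve 99% power at the 0.05 significance level to detect a difference in incidence rates of at least 1" when the Suboxone rate is 2 per 1 000 patient-days.

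**The concern.** A Poisson model treats every counted day as a separate event. Here the independent events are at best visits and admissions, and an admission brings a run of consecutive days. A patient's count is therefore a sum of clumps, and its variance exceeds its mean. A severity covariate does not remove clumping within a stay. The model-based standard errors are too small, p-values too low and intervals too narrow.

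Section 14.1 intends this endpoint to persuade policy makers and insurers to fund the more expensive drug. With about 33 expected days per arm, one long admission could decide the result. Section 17 leaves the data analysts unmasked, so a correction chosen after seeing results by arm would be open to challenge.

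**Working it through.** **1. The plan's own power figure.** Inputs (Section 14.4 and Table 4): 2 versus 1 day per 1 000 patient-days; 20 × 365 × 0.5 = 3 650 patient-days per group; two-sided 5%.
- Expected days: 7.3 and 3.65. Normal approximation, independent days: (7.3 − 3.65)/√(7.3 + 3.65) = 1.10; power = Φ(1.10 − 1.96) ≈ 20%. Exact calculation for the score test: 17.7%.
- At 45 × 365 = 16 425 patient-days per arm: 32.85 versus 16.43 days, power about 65%.
- The stated 99% does not reproduce. Power near 100% appears only if the rates are entered per patient-day instead of per 1 000 patient-days.

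**2. Dispersion.** Let L be the days contributed by one episode. If episodes are Poisson, variance/mean of the day count is φ = E[L²]/E[L]. With 622 visits of 1 day and 128 admissions of 3 days (Section 5.1.2):
φ = (622 + 128 × 9)/(622 + 128 × 3) = 1 774/1 006 = 1.763.

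**3. Type I error of the nominal 5% test.** 2[1 − Φ(1.96/√φ)] = 2[1 − Φ(1.476)] = 14.0%. In 200 000 simulated null trials (45 per arm, 365 days, 2 days per 1 000) rejection was 13.5% (Wald) and 14.1% (likelihood ratio). With every episode set to one day it was 4.8% and 5.2%, so the excess comes from the multi-day stays.

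**4. Varying the inputs, same formula.**

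| Admissions as share of episodes | Every stay 3 days | Half 1 day, half 3 days (lowest φ with a median of 3) |
|---|---|---|
| 128/750 = 17% | φ 1.76, 14.0% | φ 1.44, 10.2% |
| 10% | φ 1.50, 11.0% | φ 1.27, 8.2% |
| 5% | φ 1.27, 8.2% | φ 1.14, 6.7% |

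All of these ignore stays longer than 3 days and differences between patients.

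**5. One stay.** 16 425 × 2/1 000 ≈ 33 days per arm. If both arms have 33 and one patient has a further 19-day stay, z = ln(52/33)/√(1/52 + 1/33) = 2.04, p = 0.041.

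**6. Candidate corrections.** Null simulations, about 2 000 trials per case: 90 patients, blocks of 6 within clinic × severity, model with treatment and severity. Clinic and severity shares and a severity rate ratio of 1.5 are assumed. The first row uses the Section 5.1.2 mix with 3-day stays. The other rows are illustrative, because the documents give neither the stay distribution nor the between-patient variance. The last column is power for 2 versus 1 per 1 000 at 45 per arm.

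| Case | Poisson | Pearson-scaled, t | Sandwich | Stratified permutation | Power, Pearson-scaled |
|---|---|---|---|---|---|
| 3-day stays | 13.8% | 5.1% | 6.0% | 4.3% | 41% |
| 3-day, gamma heterogeneity (variance 2) | 24.9% | 4.6% | 6.1% | 4.1% | 26% |
| Lognormal stays, median 3, log-SD 0.8 | 31.0% | 5.4% | 9.2% | 4.0% | 32% |
| Lognormal, log-SD 1.0 | 39.0% | 5.8% | 11.9% | 4.3% | 30% |
| Lognormal, log-SD 1.0, plus gamma | 44.1% | 4.2% | 9.7% | 3.3% | 20% |

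Under the null and under a halved rate, nominal 95% intervals for the rate ratio covered 56–87% (Poisson), 94–96% (Pearson-scaled) and 85–94% (sandwich).

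**The case against.** The strongest reply is that Section 20.11b does not state a variance estimator, so a robust or scaled one could still be used, and that 14% is a scenario rather than a trial estimate. The 622:128 ratio describes regional care in 2020, not patients stabilised on treatment. The stay length is cited to a provincial costing source with a narrower code set than Section 12.12 uses. With 5% admissions and the shortest stays compatible with a median of 3, the error is only 6.7%. The larger percentages rest on assumed inputs. Nineteen days is the shortest added stay that crosses 0.05 (18 days gives p = 0.051), and under the lognormal cases only about 1–3% of stays are that long. Several corrections would be valid.

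Much of this stands as a limit on precision. The exact inflation is unknown, the skewed and heterogeneous cases are illustrations, and the 19-day stay shows sensitivity, not likelihood. It does not remove the problem. A Poisson regression named without any variance option means model-based errors, and every case examined exceeds 5%. The 6.7% and 8.2% floors exclude the long tail that Section 5.1.2 itself reports. It is also fair that the power failure is a separate fault, since it arises with independent days; it is raised here because any restated figure must allow for overdispersion.

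**Conclusion.** The analysis is wrong as written. Under Section 20.11b the test on a primary endpoint does not hold its 5% level. The error is about 14%, given the Section 5.1.2 mix, every stay of 3 days and no differences between patients; at that mix a median stay of 3 days keeps it above about 10%. If admissions are only 5–10% of episodes, it is about 7–11% on the fixed-stay assumptions. Skewed stays or patient heterogeneity raise it, to 25–44% in the illustrative cases. The direction is certain; the size depends on trial data not yet seen. The 99% power figure fails independently of this.

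**What to change.** In Section 20.11b:
- Keep the Poisson rate ratio as the point estimate, with one count per patient and time alive as exposure.
- Prespecify Pearson dispersion-scaled standard errors with a t reference for the primary test and its interval. Derive the rate difference, which Section 12.12 names as the outcome, from the same scaled model.
- Prespecify as a sensitivity analysis a permutation test that shuffles patients within clinic × severity. A negative binomial model can be another.
- Do not rely on sandwich errors alone: rejection was 6.0% with fixed 3-day stays but 9–12% with skewed stays.

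In Sections 14.3 and 14.4, withdraw the 99% figure and restate power allowing for overdispersion.

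The analysis change needs SAP wording and one model option, and no new data. Its costs are real. Intervals widen about 1.3-fold (√1.763) with fixed 3-day stays and 1.6- to 2.3-fold in the illustrative cases. The scaled rate-difference interval covered 91–95% in unstratified simulations, slightly short when stays are skewed. Power at 45 per arm with full follow-up is about 41% with fixed 3-day stays and 20–32% in the illustrative cases. If that leads to a larger sample, Section 25 requires a formal amendment with ethics approval; otherwise the protocol should say openly that this endpoint is underpowered.
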